### 9.5. Follow Up

Participants will be requested to complete a Follow-Up Visit 1 week after the end of the treatment period (Day 14 for Part A and Day 9 for Part B). The focus of this visit will be completion of safety assessment and monitoring of AE's and Concomitant medications.

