## 20.7. Recording of adverse events

For Australian sites, all events from Screening to prior to the first dose of IMP will be captured as medical history. All events occurring during and following the first administration of IMP will be reported as AEs or SAEs (if criteria met) until the completion of the End of Study Evaluation visit.

AEs that are ongoing at the End of Study Evaluation visit will be followed up until the event has resolved or stabilised. All follow-up information will be recorded in the participant's source records. All spontaneously volunteered and enquired for, as well as observed AEs, will be recorded in the participant's source records as well as the CRF.

It is preferable that AEs and SAEs be reported as diagnoses if available, rather than individual signs and symptoms. SAEs should be reported and documented in accordance with the procedures in listed below. The following data should be documented for each AE: the description of the event, start and stop dates, intensity, causality and outcome must be recorded, as well as any actions taken.

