#### 21.3.2. Adverse events

Adverse events will be coded using the Medical Dictionary for Regulatory Activities (MedDRA) (Version 20.0 or later) and summarised by system organ class (SOC) and preferred term (PT).

A summary of the number and percentage of participants with the following adverse events will be prepared for Part A: by dose (with all placebo subjects combined) and overall; Part B: by treatment within sequence, by treatment and overall :

- All adverse events
- Serious adverse events
- Adverse events leading to premature discontinuation of IMP
- Adverse events by intensity
- Adverse events by relationship to IMP

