2. PROJECT OVERVIEW

2.1 Study Design

This is a Proof-of-Concept study that consists of two parts

2.1.1 *Part A (single ascending dose study)*

Part A will be a double-blind, randomized, placebo-controlled, single ascending dose (SAD) study within 8 healthy volunteers of intravenous administration of LAT8881 over 5 minutes.

The SAD study will enrol 8 participants and each participant will have three treatment days, 1 infusion per dosing day on days 1, 4 and 7 as well as two short visits for safety blood sampling on

[figure not shown]
Day 3 and 6 (Figure 1). The 8 participants will be split into two groups of 4 participants each (3 IMP and 1 placebo), with the two groups dosed a few days apart.

Participants will arrive on the morning of each treatment day, receive a single infusion, leave that afternoon (no overnight stay). Participants on a given dosing day will be dosed at staggered intervals as determined by PI.

Treatments will be on Days 1 (0.8 mg/kg), Day 4 (1.2 mg/kg) and Day 7 (1.8 mg/kg) or placebo to allow sufficient washout and consideration of any safety observed following each dosing day. Day 3 and 6 safety blood results will be reviewed prior dosing on the following dosing day.

Participants will fast for 8 hours pre-dose and 4 hours post dose for each dosing occasion. Participants will be randomised, so on each treatment day per group, 3 participants receive LAT8881 and 1 receive placebo (different participants to receive placebo each treatment day). Participants will remain at the clinic until 6 hours post-infusion in order to collect blood samples for PK analysis and for review of safety and tolerability. Safety assessments will be reviewed in a clinic exit visit 7 days after the last infusion.

Figure 1: Part A Study Design

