3.2.5 Treatment groups – Part A

Tabulations will summarize data by treatment group, the pooling of all the study drug, and total (all groups). All placebo participants will be grouped in a single cohort for tabulation summaries.

For Part A, treatment groups within tables are planned to be presented as:

LAT8881 (0.8mg/kg) (N=X)	LAT8881 (1.2mg/kg) (N=X)	LAT8881 (1.8mg/kg) (N=X)	LAT8881 (All Doses) (N=X)	Placebo (N=X)	Total (N=X)
--------------------------------	--------------------------------	--------------------------------	---------------------------------	------------------	----------------

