12.1 Adverse Events (AEs)

AEs will be coded using the current version of the Medical Dictionary for Regulatory Activities (MedDRA, version 24.1) by system organ class (SOC) and preferred term (PT), classified from verbatim terms.

All AEs recorded during the study will be listed, grouped by participant and treatment group.

A Treatment Emergent Adverse Event (TEAE) is defined as any untoward medical occurrence reported or observed after the start of dosing with study drug and prior to the End of Study visit. Conditions present before the first dose of study drug that increase in severity after the first study drug administration will also be considered TEAEs. Where an AE start date is partially or fully missing, and it is unclear as to whether the AE started after treatment administration, it will be assumed to be a TEAE.

AE summaries will be restricted to TEAEs only.

An overview summary table of TEAEs will be provided for:

- Part A by treatment group and overall
- Part B by treatment within sequence, by treatment and overall

Table will include number of participants reporting at least one of the following:

- TEAE
- Grade 3+ TEAE
- Related TEAE
- Serious TEAE
- Serious and related TEAE

Number of participants discontinued from treatment due to a TEAE

Number of participants withdrawn from the study due to a TEAE

Number of deaths

For the TEAE summaries, participants who experience the same TEAE more than once will be counted only once for that event within each category (PT, SOC or overall).

The number and percentage of participants experiencing a TEAE, will be summarised for each SOC and PT by cohort and overall for the following categories of events, by severity:

- All TEAEs
- All TEAEs related to the study drug
- All Grade 3+ TEAEs
- All serious TEAEs
- All serious TEAEs related to the study drug

The number and percentage of participants experiencing a TEAE will be summarised for each SOC and PT by maximum severity and cohort for all TEAEs and all TEAEs related to study medication. If a participant experiences the same AE at more than one severity grade, the most severe rating or the stronger causal relationship to investigational product will be given precedence. Only severities that are populated will be reported.

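### Part A TEAE percentages by dose have no event-to-dose rule and no common post-dose window, so unequal follow-up alone can raise the 1.8 mg/kg column in one step

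*SAP*

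**What the plan says.** Part A gives the doses in a fixed ascending order (SAP 2.1): "Treatments will be on Days 1 (0.8 mg/kg), Day 4 (1.2 mg/kg) and Day 7 (1.8 mg/kg) or placebo". On each day six participants receive LAT8881 and two receive placebo, with different participants on placebo each time (SAP 2.1.1 and 2.2). For the end of follow-up, SAP 2.1 states: "Safety assessments will be reviewed in a clinic exit visit 7 days after the last infusion". Protocol 9.5 places that visit "1 week after the end of the treatment period (Day 14 for Part A and Day 9 for Part B"), and the Part A schedule allows 2 days either side.

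Collection is continuous. Under Protocol 20.7, events from the first dose onward "will be reported as AEs or SAEs (if criteria met) until the completion of the End of Study Evaluation visit". SAP 12.1 defines a TEAE as "any untoward medical occurrence reported or observed after the start of dosing with study drug and prior to the End of Study visit", with no limit in hours or days after an infusion.

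For the table columns, SAP 3.2.5 says "Tabulations will summarize data by treatment group, the pooling of all the study drug, and total (all groups", with all placebo participants in one column. Protocol 21.3.2 asks for adverse events "by dose (with all placebo subjects combined) and overall", and SAP 12.1 for an overview "Part A by treatment group and overall". The measure is participants with an event, as a count and percentage. SAP section 3 makes the denominator subjects. No rate per unit of time is planned.

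SAP 3.2.6 assigns each event to a treatment by its start date, but that section covers Part B. Section 3.2.5 has no equivalent for Part A.

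**The concern.** Every Part A participant passes through all three dosing days, so each event has to be allotted to one of several treatments, and the SAP does not say how. The natural reading is to carry over the Part B rule. Each column then collects events from its infusion until the next one, and for the Day 7 infusion until the exit visit. Because dose is tied to day, everyone given 1.8 mg/kg has the long interval and nobody on a lower dose has it. Randomising who receives placebo on each day cannot balance this. In the pooled placebo column, only the two participants given placebo on Day 7 have the long interval.

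At stake is the reading of the Part A primary endpoint, where adverse event incidence and severity are set side by side for the ascending doses. An inert product could appear less well tolerated at the top dose, and the two lower doses could appear slightly better tolerated than placebo. Nothing in the planned tables would alert the reader.

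**Working it through.** The documents give no adverse event incidence or power figure for Part A, so there is no stated figure to reproduce.

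**Inputs from the documents.** Infusions on Days 1, 4 and 7 (SAP 2.1). Exit visit on Day 14 (Protocol 9.5), plus or minus 2 days (Part A schedule). Six active and two placebo participants per dosing day (SAP 2.2).

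**Assumptions.** Each event goes to the most recent infusion before onset. The background risk is not in the documents, so it is varied.

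**Step 1: follow-up per column.**
- 0.8 mg/kg: 4 − 1 = 3 days, 6 × 3 = 18 person-days
- 1.2 mg/kg: 7 − 4 = 3 days, 18 person-days
- 1.8 mg/kg: 14 − 7 = 7 days (5 to 9 with the tolerance), 42 person-days
- Placebo: 2×3 + 2×3 + 2×7 = 26 person-days over 6 participants, mean 4.33 days

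**Step 2: expected events per participant under a constant hazard.** Top dose against either lower dose: 7/3 = 2.33. Top dose against placebo: 7/4.33 = 1.62. Lower doses against placebo: 3/4.33 = 0.69.

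**Step 3: participants with at least one event.** Incidence over t days at rate h is 1 − exp(−h·t). For placebo it is (2 × 3-day value + 7-day value)/3.

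| Assumed events per day | 0.8 and 1.2 mg/kg | 1.8 mg/kg | Placebo | Expected participants of 6, lower dose vs top | Difference |
|---|---|---|---|---|---|
| 0.02 | 5.8% | 13.1% | 8.2% | 0.35 vs 0.78 | 0.43 |
| 0.05 | 13.9% | 29.5% | 19.1% | 0.84 vs 1.77 | 0.94 |
| 0.10 | 25.9% | 50.3% | 34.1% | 1.56 vs 3.02 | 1.47 |

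Expressed through the 3-day risk p3, the 7-day risk is 1 − (1 − p3)^(7/3). The ratio is 2.26 at p3 = 5%, 2.18 at 10%, 2.03 at 20%, 1.88 at 30% and 1.60 at 50%. It is at least 2 while p3 is no more than about 22%. At p3 = 10%, moving the exit visit within its tolerance gives 1.61 (5 days) to 2.71 (9 days).

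**Step 4: risk concentrated on the dosing day.** Let H = −ln(1 − p3) and let a share f of H fall on the dosing day, which all doses share. The rest covers two further days at the lower doses and six at the top dose, so the top-dose cumulative hazard is fH + 3(1 − f)H. With f = 1/3 this is the constant-hazard case.

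| p3 | f = 1/2 | f = 3/4 |
|---|---|---|
| 10% | 1.90 | 1.46 |
| 20% | 1.80 | 1.42 |
| 30% | 1.70 | 1.38 |

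**Step 5: how often a reader would see it.** At p3 = 20% with constant hazard and six per column, the top dose shows more affected participants than 0.8 mg/kg with probability 0.69 and fewer with probability 0.13. This treats the columns as independent, although they share participants.

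**Step 6: another assignment rule.** Counting an event under every dose already given makes the intervals 14 − 1 = 13, 14 − 4 = 10 and 14 − 7 = 7 days. They are still unequal, now longest for the lowest dose. So the direction of the distortion depends on a rule the SAP does not state.

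**Step 7: common interval.** With three days counted after each infusion, every column has 3 days per participant, and an equal background hazard gives a ratio of 1.00.

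**The case against.** The strongest reply is that little depends on these percentages. The analysis is descriptive, with no dose-trend test and six participants per dose. The MTD rule in Protocol 7.3 counts dose-limiting toxicities, and the stopping rules in 17.2 count drug-related or possibly allergic events. SAP 12.1 also tabulates related TEAEs separately, and late background events should often be judged unrelated. All events are listed, and SAP section 12 replaces tables with a paragraph if data are sparse. All of this stands and limits the consequence. It does not correct the all-TEAE percentages.

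The timing of ascertainment also counts against a large effect. The Part A schedule has adverse event review at ten post-dose times on each dosing day, none on Days 3 and 6, and one at Day 14. Reporting may therefore cluster on dosing days, which every dose shares. Step 4 allows for this: the ratio shrinks but stays above 1.

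A reader might infer three stronger things that the documents do not support:
- **A false graded dose trend.** The two lower doses have equal intervals, so the artefact is flat and then rises once.
- **A doubled incidence as a fact.** That needs both the assumed assignment rule and a roughly constant hazard.
- **A distorted choice of Part B dose.** SAP 3.2.6 already sets 1.8 mg/kg and SAP 2.5 reports 14 Part B completers. The artefact would have made the selected dose look worse.

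**Conclusion.** The point holds as a defect in how the Part A safety tables are specified. The plan has neither an event-to-dose rule nor a common post-dose interval, while follow-up per column is nominally 3, 3 and 7 days, and 4.33 days on average for placebo. From background events alone, the 1.8 mg/kg column would stand at up to 2.33 times the lower doses under a constant hazard, or about 1.4 to 1.9 times if half to three quarters of the 3-day risk (10% to 30%) falls on the dosing day. In counts this is less than one extra participant in six at 0.02 to 0.05 events per day, and about 1.5 at 0.10.

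These sizes rest on assignment to the most recent infusion, on assumed background rates, and on the nominal Day 14 visit. The effect is confined to the descriptive reading of the Part A primary safety endpoint in the report. No error rate is affected, and neither are the Part B tables. It should be corrected because the remedy is small and the table is the main display of that endpoint.

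**What to change.** In SAP 3.2.5 and 12.1:

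1. State that each Part A TEAE is assigned to the most recent infusion before onset. Add a convention for events dated on an infusion day when it is not recorded whether they began before or after the infusion.
2. Keep the full-period table by dose, and footnote the unequal follow-up: 3, 3 and 7 nominal days, and 4.33 on average for placebo.
3. Add a by-dose and placebo summary limited to onset from the infusion through the second calendar day after it, and before the next infusion: Days 1-3, 4-6 and 7-9.
4. Show events starting later after the Day 7 infusion in a separate row, by Day 7 treatment.

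Calendar days are preferable to a 72-hour cut. Protocol 20.7 requires start and stop dates but not onset times, and staggered dosing could make two 72-hour intervals overlap. Keeping the full-period table means no late event after the top dose leaves the main display.

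The cost is SAP wording, one derived flag and one extra table or set of rows, with no new data collection. Protocol 21.1 schedules the Part A analysis when Part A completes, so if those outputs already exist the added summary should be labelled post hoc.

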3.2.6 Treatment groups – Part B

LAT8881 will be administered at a dose of 1.8 mg/kg via an infusion pump at a constant rate over 10 minutes.

The placebo formulation will be presented as above but without the LAT8881 active.

Tabulations for part 2 will summarise data as follows:

Demographics and baseline characteristic data, will be summarised by:

- LAT8881 1.8 mg/kg /Placebo
- Placebo/LAT8881 1.8 mg/kg
- Total

Visit based tabulations will be summarised by treatment received (LAT8881 1.8 mg/kg or Placebo) and total, and timepoint relative to within period dosing. Treatment will be assigned to individual records based on the treatment period. Timepoints will be:

- Screening (summarised as total only)
- Day 1- predose/Day 2-predose (combination of Day 1 and Day 2, summarised by treatment)
- Day 1- dose/Day 2-dose (combination of Day 1 and Day 2, summarised by treatment)
- Day 1- 5min/Day 2-5min (combination of Day 1 and Day 2, summarised by treatment)
- Day 1- 10min/Day 2-10min (combination of Day 1 and Day 2, summarised by treatment)
- Day 1- 15min/Day 2-15min (combination of Day 1 and Day 2, summarised by treatment)
- Day 1- 20min/Day 2-20min (combination of Day 1 and Day 2, summarised by treatment)
- Day 1- 30min/Day 2-30min (combination of Day 1 and Day 2, summarised by treatment)
- Day 1- 45min/Day 2-45min (combination of Day 1 and Day 2, summarised by treatment)
- Day 1- 1hr/Day 2-1hr (combination of Day 1 and Day 2, summarised by treatment)
- Day 1- 1.5hr/Day 2-1.5hr (combination of Day 1 and Day 2, summarised by treatment)
- Day 1- 2hr/Day 2-2hr (combination of Day 1 and Day 2, summarised by treatment)
- Day 1- 2.5hr/Day 2-2.5hr (combination of Day 1 and Day 2, summarised by treatment)
- Day 1- 3hr/Day 2-3hr (combination of Day 1 and Day 2, summarised by treatment)
- Day 1- 3.5hr/Day 2-3.5hr (combination of Day 1 and Day 2, summarised by treatment)
- Day 1- 4hr/Day 2-4hr (combination of Day 1 and Day 2, summarised by treatment)
- Day 1- 5hr/Day 2-5hr (combination of Day 1 and Day 2, summarised by treatment)
- Day 1- 6hr/Day 2-6hr (combination of Day 1 and Day 2, summarised by treatment)
- Day 9/ETV (summarised as total only)

○ Event based tabulations (e.g. adverse events, concomitant medications and deviations) will be summarised by treatment and total. Treatment will be assigned to individual records based on the treatment period of the start date of the event.

- Adverse Events:
 - Events started prior to the Day 1 study drug administration will only be considered as Medical History.
 - If start date is after Day 1 study drug administration, then it will be assigned to the treatment received in Period 1.
 - If start date is after the Day 2 study drug administration, then it will be assigned to the treatment received in Period 2.
- Protocol Deviations:
 - If date is before Day 1 then it will be assigned to Screening
 - If date of deviation is after Day 1 study drug administration, then it will be assigned to the treatment received in Period 1.
 - If start date is after the Day 2 study drug administration, then it will be assigned to the treatment received Period 2.
- Concomitant Medications:

- Based on start and end dates – if subject was on medication within a given period then that medication will be summarised within that period. If subject took medication across both periods then it would be counted in both treatment columns.
- Treatment Exposure will be summarised by sequence and total

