2.1.2 Part B (Cross-Over Study)

Part B will be a placebo-controlled randomized double blind cross-over safety and efficacy study of LAT8881. Up to 20 participants will be randomized into two groups and will receive either a single dose of LAT8881 [the dose selected from Part A of the study] or placebo via intravenous administration over 10 minutes on two consecutive days.

Participants will be randomly assigned to one of two groups, active then placebo or placebo then active (Figure 2).

After passing screening, participants will be admitted for two nights:

1. A study staff member will contact the participant for 3 consecutive days to obtain a verbal pain score out of 10 to confirm that their mean resting radicular pain meets the study inclusion criteria (pain score on each of the 3 days must be ≥ 3)
2. The participant will arrive the evening prior to dosing, and will complete a final review of inclusion/exclusion criteria.
3. Baseline assessments will be completed on the first day of dosing prior to IMP administration
4. The participant will then receive their first dose.
5. Collection of blood samples for PK/ PD analysis and assessments for review of safety, tolerability and efficacy are listed in the Schedule of Assessments.

The participants will stay overnight.

If the PK from the Part A demonstrates elimination in <6 hours (assessed by concentration below LOQ of assay),

[figure not shown]
6. The following morning the participants will cross-over and receive their second dose.
7. Collection of blood samples for PK analysis and assessments for review of safety, tolerability and efficacy are listed in the Schedule of Assessments.
8. Participants will remain at the clinic until 6 hours post the second infusion and then may be discharged.

At the discretion of the Investigator and in consultation with the Study Sponsor, the requirement for subjects to be admitted to the clinic from the evening before Day 1 through to discharge at the end of Day 2 can be waived. In such circumstances, items 1 through 8 above will still apply, with the following modification to item #2:

- During the morning of Day 1 the following will be undertaken prior to dosing: a) a complete final review of inclusion/exclusion criteria, b) a written account of the activities the participant undertook on Day 0.
- Prior to dosing on Day 2, a written account of the activities the participant undertook after discharge at the end of Day 1.

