2.4.2 Secondary Endpoints

Part A

- Pharmacokinetic profile

Part B

- Comparison of radicular “pain now” scores as peak change from baseline and area under the curve comparing the two arms over the full six hours
- Comparison of patients’ general impression of change between dosing arms
- Adverse event rates in each dosing arm

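### Part B adverse events are labelled over unequal windows (about 1 day v about 7 days), so the pooled LAT8881–placebo comparison is informative only for onset within about 24 hours of dosing

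*SAP*

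**What the plan says.** SAP 3.2.6 states the basis of assignment: "Treatment will be assigned to individual records based on the treatment period of the start date of the event". For Period 1, "If start date is after Day 1 study drug administration, then it will be assigned to the treatment received in Period 1", which I read as running up to the second infusion. For Period 2, "If start date is after the Day 2 study drug administration, then it will be assigned to the treatment received in Period 2". No upper time limit is given. SAP 12.1 counts treatment-emergent events up to the End of Study visit, and SAP 2.1.2 places the exit visit 7 days after the last infusion (Day 9 in Protocol 9.5). The infusions are given "via intravenous administration over 10 minutes on two consecutive days".

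The comparison matters because a Part B secondary endpoint in SAP 2.4.2 is "Adverse event rates in each dosing arm". SAP 12.1 and Protocol 21.3.2 plan the adverse event summaries by treatment within sequence, by treatment, and overall. For visit-based tables, SAP 3.2.6 reports Day 9 in total only and attributes it to neither treatment.

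On pre-existing conditions, SAP 3.2.6 says "Events started prior to the Day 1 study drug administration will only be considered as Medical History", while SAP 12.1 says "Conditions present before the first dose of study drug that increase in severity after the first study drug administration will also be considered TEAEs".

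**The concern.** The two treatments are not observed for the same time. Whichever is given first has about one day before its label ends; whichever is given second keeps its label for about a week. In the LAT8881-then-placebo sequence, an event starting between the second infusion and Day 9 is booked to placebo even if it is a delayed effect of LAT8881. In the other sequence the same kind of event is booked to LAT8881.

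With balanced sequences, late-onset LAT8881 events therefore add about equally to both columns of the pooled table. A reader of that table could take similar late rates as evidence that LAT8881 and placebo are alike, when the layout would give that picture at any late risk. Background events during the week of follow-up also enter both columns.

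A smaller point sits in the same section. Because assignment uses the start date, a condition that began before dosing and worsened afterwards counts as treatment-emergent under SAP 12.1 but has no stated period under SAP 3.2.6.

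**Working it through.** The documents give no figure for this comparison, so there is none to reproduce. The check is expected-count arithmetic on the four sequence-by-period cells.

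**Inputs**
- Period 1 window: about 1 day (consecutive-day infusions, SAP 2.1.2).
- Period 2 window: about 7 days (SAP 2.1.2 and 12.1).
- Sequence sizes: 10:10 planned (SAP 2.2). SAP 2.5 expects 17 completers at closure, so 9:8 is the most even split.
- Adverse event risks: none are stated. Let *e* be the risk of a LAT8881 event starting before the next infusion, and *d* the risk of one starting later but before Day 9. All values of *e* and *d*, and the 11:6 split, are assumptions.

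**Step 1: columns.** Let n1 be the number given LAT8881 first, n2 the number given placebo first, and N = n1 + n2. Leaving background aside and adding early and late events:
- LAT8881 column = [n1·e + n2·(e + d)] / N
- Placebo column = n1·d / N
- Difference = e + d·(n2 − n1)/N, whereas the true excess is e + d

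**Step 2: numbers**

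| n1:n2 | e | d | LAT8881 | Placebo | Shown difference (points) | True excess (points) |
|---|---|---|---|---|---|---|
| 10:10 | 0 | 0.10 | 5% | 5% | 0 | 10 |
| 10:10 | 0 | 0.30 | 15% | 15% | 0 | 30 |
| 10:10 | 0 | 0.50 | 25% | 25% | 0 | 50 |
| 10:10 | 0.20 | 0.20 | 30% | 10% | 20 | 40 |
| 9:8 | 0 | 0.30 | 14.1% | 15.9% | −1.8 | 30 |
| 8:9 | 0 | 0.30 | 15.9% | 14.1% | +1.8 | 30 |
| 11:6 | 0 | 0.30 | 10.6% | 19.4% | −8.8 | 30 |

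At 9:8 or 8:9 the residual is d/17 in size, or 5.9% of d. The early risk *e* is estimated correctly in every row where d is zero or the sequences are equal.

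**Step 3: limits of the equality**
- It holds in expectation only. At 10:10 with d = 0.30, the SD of the difference is √(20 × 0.3 × 0.7)/20 = 10 points. In 200,000 simulated trials it was exactly zero in 19%.
- It needs both infusions. If 1 or 2 of 10 LAT8881-first participants never receive the second infusion, their late events stay under LAT8881. At d = 0.30, keeping 20 as the denominator, the residual is +3 or +6 points.
- Late events can be seen for about 7 days in LAT8881-first participants (days 1 to 8 after LAT8881) and about 6 in placebo-first participants (days 1 to 7). At an assumed constant hazard *h*, the residual at 10:10 is ½[(1 − exp(−6h)) − (1 − exp(−7h))]. That is −0.9 points at h = 0.02 per day and −1.8 points at h = 0.05.

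**Step 4: background.** Mean observation per treatment is (1 + 7)/2 = 4 days. At a constant background rate, each column holds about four times the background of a one-day window. At 10:10 both columns gain the same amount, so this adds noise rather than bias.

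**Step 5: can another label recover d?** Order the cells as LAT8881-first Period 1, LAT8881-first Period 2, placebo-first Period 1, placebo-first Period 2. The indicator for extra Period 2 background is (0, 1, 0, 1). The indicator for a late LAT8881 effect is also (0, 1, 0, 1). With an intercept and an early-effect term, the four-column matrix has rank 3. The late effect is aliased with Period 2, and no assignment rule separates them.

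**Step 6: worsened conditions.** SAP 3.2.6 confines a pre-dose onset to medical history. SAP 12.1 makes its post-dose worsening treatment-emergent. Protocol 20.1 includes worsening of a pre-existing condition in the definition of an adverse event, and Protocol 20.7.1 does the same for clinically significant baseline abnormalities that worsen. The intent is clear, but SAP 3.2.6 does not say which date places the worsening in a period.

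**The case against.** A reader might infer that every late LAT8881 event cancels out and that the drug signal is erased. The documents do not support that. Each event is counted once, and only the expected pooled difference is near zero. The planned summaries by treatment within sequence would show late events as a Period 2 excess in both sequences. SAP 3.2.4 groups listings by sequence, and Protocol 20.7 records start date, stop date and causality for each event, so late events after LAT8881 remain traceable. What stands against the plan is that the Period 2 excess still carries a treatment label and cannot be told apart from the longer window.

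A reader might also infer that the labelling rule causes the loss and that better labelling would restore it. Step 5 shows otherwise: the one-day interval between infusions causes the aliasing. The label only makes the pooled table look like a treatment comparison for events it cannot compare.

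It can also be said that the safety analysis is descriptive, that SAP 12 allows a narrative if data are few, and that next-day crossover depends on elimination within 6 hours in Part A. These points limit the weight. The elimination condition concerns plasma concentration, though, and sets no limit on event onset. No document supports a particular late risk, and none excludes one; the plan itself collects events to Day 9.

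On worsened conditions, the Protocol definitions largely answer the point. A clarifying phrase is all that is missing.

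**Conclusion.** The concern holds in a limited form. The pooled by-treatment comparison of adverse events in Part B is informative only for onset before the next infusion, about 24 hours. Later LAT8881 events fall about equally into both columns in expectation: exactly so at 10:10 with both infusions given and equal late risk in the two sequences, and with a residual of about 6% of the late risk at 9:8. Under assumed early and late risks of 0.20 each, the table would show a 20-point difference against a true excess of 40.

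Early-onset events are compared correctly, and late events are not hidden from someone who reads the within-sequence tables and listings. The fault is a misleading placebo attribution in a named secondary endpoint. It is also at odds with SAP 3.2.6's own practice of leaving Day 9 visit data unattributed. The conflict over worsened conditions is real but minor.

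**What to change.** 1. Base the by-treatment comparison of treatment-emergent events on an equal post-dose window. In Period 1, count onset from the start of the infusion to the next infusion; in Period 2, count onset over the matching interval of about 24 hours.
2. Show all later events by sequence, with the last treatment received, and in total. Include late events in participants who received only the Day 1 infusion, a case that Protocol 17.1 foresees, so that no event lacks a column.
3. Keep the planned all-event tables by treatment within sequence. Add a footnote that the windows are unequal and that late events cannot be attributed to one treatment. Late or serious events after LAT8881 then stay visible.
4. In SAP 3.2.6, assign a worsened pre-existing condition to the period containing the date of worsening, to agree with SAP 12.1.

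This takes SAP wording and one extra table, with no new data and no change to conduct. The price is fewer events in the main by-treatment comparison. These include some late events after LAT8881 in placebo-first participants that the present rule counts under LAT8881, which is why item 3 is needed. The change removes a misleading comparison; it does not make a late effect estimable.
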